10.8.3.2 Exposure during pregnancy and recording and reporting of birth events

Pregnancies must be reported throughout the study, including up to 4 weeks after the last dose of the study drug received. Pregnancy reporting includes exposure of the female partner of a male participant. Although pregnancy is not considered an AEFI, it must be reported within 24 hours of notification by the participant. Pregnancy complications are reported as AEs or SAEs (if applicable). All pregnancies will be followed through delivery to record any SAEs. Deaths, spontaneous or elective abortions, congenital anomalies/birth defects, and AEs/SAEs occurring in newborns must be reported as SAEs. Newborns potentially exposed to the study drug through

maternal or paternal sources who present with an AEFI before, during, or after delivery (including those who were breastfed by the participating mother) will be followed up until the event is resolved (or for a period of 1 year).

11 STUDY COMMITTEES

11.1 Data Monitoring Committee (DMC)

An independent DMC will be established, composed of scientists of good reputation and experience, with no involvement in this research protocol. The DMC will act as a research advisor to monitor the safety of participants in this study. The DMC is governed by a charter that outlines the working procedures and responsibilities of the DMC. The Steering Committee will define the working procedures and responsibilities of the DMC. The charter will be agreed upon in advance by the DMC and will adhere to good research practices.

11.2 Event Adjudication Committee

The independent Event Adjudication Committee (EAC) will evaluate all events related to the study outcomes based on pre-established criteria in a prospective and blinded manner. EAC members must not be directly involved in the research and must include at least two qualified members. The EAC will not be aware of the study's treatment assignments when evaluating events. Outcome adjudication will occur continuously throughout the blinded treatment phase of the study.

12 STATISTICAL CONSIDERATIONS

12.1 Study Design

This study is a randomized, adaptive-platform Phase III clinical trial. The study evaluates the efficacy and safety of novel and repurposed therapies (investigational products [IPs]) in participants with symptoms of chronic fatigue from long COVID-19 following resolution of acute COVID-19 infection. This study evaluates various IPs for chronic fatigue syndrome from long COVID-19 under a common platform.

12.1.1 Internal Pilot Phase

Due to the rapidly evolving knowledge regarding LONG COVID, it is necessary to assess various aspects related to the study's feasibility that need to be evaluated as soon as we begin implementation.

The objective of the internal pilot phase is to identify and resolve any unforeseen feasibility issues to enhance the overall success of the research. In particular, we will assess issues related to recruitment, informed consent, medication availability and administration, and data collection and recording. There will be no analysis of clinical results at the end of this phase—since participants will be transferred to the main study and analyzed collectively. This will involve a blinded analysis of up to 10% of the target sample size, with an initial focus on the safety and tolerability of the investigational products under evaluation.

12.1.2 The Main Clinical Study

This phase involves the full implementation of the clinical trial, with the primary clinical endpoint being a reduction in perceived fatigue on the Fatigue Severity Scale (FSS). This phase is also an adaptive phase, with three interim analyses to evaluate the effects against the placebo arm. The main adaptations include:

- I. Discarding the placebo arm if there is strong evidence of benefit.
- II. Discard active study arms that show statistically unfavorable results.
- III. Partnering with study arms of common interest from other study platforms, with the goal of obtaining responses in less time compared to conducting the study in isolation.

- IV. Add new arms with investigational medicinal products that demonstrate significant potential for benefit in preclinical and Phase II clinical evidence (safety, tolerability, and potential dose-effectiveness).

There will be three interim analyses (at 25%, 50%, and 75% of the proposed sample size of 1,500 participants, with 500 participants per intervention arm) to assess the effects of the proposed interventions compared with the placebo arm.

12.2 Randomization

Participants will be randomly assigned to one of the study arms in an equal allocation (e.g., 1:1:1). Stratified permuted block randomization will be used for this study. Randomization will be stratified by participating primary care facility with varying block sizes of participants. We will use a computer-generated interactive voice/web response system to implement randomization. For each active drug arm, there will be a placebo (or active control) arm, including for the different formulations and dosages in the study.

12.3 Sample Size Calculation I

The sample size of 500 participants per arm and its operational characteristics were confirmed using closed-form, analytical, and numerical methods. The operational characteristics for the head-to-head comparison of the treatment arm versus the placebo arm in reducing the mean fatigue score measured by the Fatigue Severity Scale (1 to 9) on day 60 are shown in Table 2. For each pairwise comparison against the placebo arm, the Type I error rate (alpha) was set at 0.025 (one-sided) using a Bayesian normal-normal model. For the planning of our study, we assumed a plausible standard deviation value of 1.7, which was estimated from a recent study that evaluated the psychometric properties of the fatigue severity scale in participants recovering from COVID-19.¹

Table 2 : Simulated operational characteristics of our study for varying sample sizes

Dropout rate	Reduction in FSS score	Sample (n = 252)	Sample (n = 500)	Sample (n = 752)	Sample (n = 1000)
0.0	0.00	2.5%	2.5%	2.5%	2.5%
	0.15	13.2%	22.6%	32.3%	41.5%
	0.30	41.8%	71.2%	87.8%	95.2%

Dropout rate	Reduction in FSS score	Sample (n = 252)	Sample (n = 500)	Sample (n = 752)	Sample (n = 1000)
	0.45	76.8%	97.1%	99.7%	100.0%
2.5	0.00	2.5%	2.5%	2.5%	2.5%
	0.15	12.9%	22.0%	31.5%	40.5%
	0.30	40.6%	69.7%	86.8%	94.7%
	0.45	75.4%	96.6%	99.7%	100.0%
5.0	0.00	2.5%	2.5%	2.5%	2.5%
	0.15	12.6%	21.6%	30.8%	39.6%
	0.30	39.5%	68.5%	85.9%	94.1%
	0.45	73.9%	96.3%	99.6%	100.0%
10.0	0.00	2.5%	2.5%	2.5%	2.5%
	0.15	12.2%	20.6%	29.4%	37.8%
	0.30	37.7%	66.1%	84.0%	92.9%
	0.45	71.5%	95.4%	99.4%	99.9%

Thus, the clinical trial will recruit 1,500 participants, divided into three groups of 500 participants each. With the proposed sample size of 500 participants in each group, the study will have adequate statistical power to detect a clinically significant treatment effect. A difference of 0.45 has been suggested as the minimum clinically important difference (MID) on the fatigue severity scale in population groups of participants with multiple sclerosis and chronic fatigue.² Even with a 10% dropout rate, our estimated power to detect a difference of 0.45 is above 90%.

During interim analyses, the unblinded statistician advising the DMC will make recommendations regarding sample size based on the ongoing evaluation of global data and epidemiological data from Brazil and the state of Minas Gerais. We are continuously monitoring the literature for new findings relevant to chronic fatigue and to participants with long-haul COVID-19.

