12.4 Statistical analysis and reporting

The analysis and reporting of results follow the CONSORT guidelines (www.consort-statement.org). The participant selection process and flow throughout the study will be summarized

using a flow diagram. The results of the analysis of participants' demographic data and baseline outcome variables (primary and secondary) will be summarized using descriptive summary measures: expressed as mean (standard deviation) or median (minimum-maximum) for continuous variables, as appropriate, and number (percentage) for categorical variables. We will adopt an intention-to-treat principle to analyze all outcomes.

Bayesian statistics is the standard statistical framework. Statistical analyses of IPs are limited to simultaneously randomized controlled data. Sequential designs with Bayesian stopping rules are expected to be used to evaluate multiple IPs. Recruitment for an IP will be stopped before the maximum sample size using pre-specified decision rules. The maximum sample size and corresponding decision rules are determined a priori by dedicated statisticians and methodologists, who will remain blinded during the conduct of the study. The statistical analysis plan (SAP) will be formulated to ensure that the expected one-sided Type I error is less than 0.025 for each treatment. We will also use multiple imputation to handle missing data. For all models, results will be expressed as the effect reported as the mean difference for continuous outcomes, odds ratios (OR) for binary outcomes, and hazard ratios (HR) for time-to-event outcomes, with their respective 95% confidence or credibility intervals.

All analyses will be performed using the latest version of R at the time of analysis. A detailed analysis plan will be developed prior to database lock. Any relevant safety data specific to Brazil will be immediately reported to our group for appropriate regulatory action.

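### Section 12.3 lets an unblinded statistician recommend sample-size changes at the interim looks, which conflicts with the a priori maximum on which the 0.025 error rate is calibrated

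*Protocol*

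**What the plan says.** **Who may touch the sample size.** Protocol Section 12.3 closes by saying that at the interim looks "the unblinded statistician advising the DMC will make recommendations regarding sample size based on the ongoing evaluation of global data and epidemiological data", the epidemiological data being those of Brazil and the state of Minas Gerais. The parallel sentence in the Overview (Sample Size row) speaks of overall rather than global data and does not say that the recommendations concern sample size. Section 12.4 says: "The maximum sample size and corresponding decision rules are determined a priori by dedicated statisticians and methodologists, who will remain blinded during the conduct". The Overview (Statistical Methods) says the same.

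**When the rules are fixed.** The Overview places the stopping rules in the SAP and describes that SAP as already formulated to keep the one-sided error below 0.025 per treatment. Section 12.4 puts the same statement in the future tense. Both then add: "A detailed analysis plan will be developed prior to database lock". The interim looks come at 25%, 50% and 75% of participants (Section 3.1).

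**What the error rate rests on.** In Section 12.3, "the Type I error rate (alpha) was set at 0.025 (one-sided) using a Bayesian normal-normal model", with 1,500 participants "divided into three groups of 500 participants each". Section 3.1 says the efficacy and futility thresholds are calibrated by simulation to 0.025 for each comparison with placebo. The Overview (Study Committee) says the DMC's analysis plan was approved before the trial began.

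**The concern.** A simulated threshold holds its error rate for the design that was simulated: a given maximum, given look times and given boundaries. Section 12.3 opens the first of these to the one person who has seen results by arm, at the moment of seeing them. It states no rule, cap or adjusted test, and does not say how the advice fits the a priori maximum in Section 12.4. Even if only external data were meant, nobody could later show that knowledge of the interim effect played no part, and external data do not need an unblinded reader.

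The dating of the plan adds to this. A detailed plan finished just before database lock satisfies the protocol's wording, although by then all three unblinded looks are over. Section 3.3.2 mentions a blinded analysis of the first 100 recruited participants, so recruitment was under way when this text was current. At stake is how far a positive result could be defended, and a moderate rise in the false-positive rate if the maximum were changed.

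**Working it through.** **Inputs (Section 12.3, Table 2; Section 3.1).** One-sided alpha 0.025; SD 1.7; difference 0.45; 500 per arm; analyses at 25%, 50%, 75% and 100%. Table 2 at n = 500 gives 2.5% at zero effect and, for 0.45, power of 97.1% (no dropout) and 95.4% (10% dropout).

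**Step 1: which design gives Table 2?** A single final test has power Φ(δ/(σ√(2/n)) − 1.96). With n = 500, σ√(2/n) = 1.7 × 0.0632 = 0.1075.
- δ = 0.45: Φ(4.185 − 1.96) = 98.7%, against 97.1% stated.
- δ = 0.30: Φ(2.790 − 1.96) = 79.7%, against 71.2% stated.

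The single-test design does not fit. Reading n as the total of a pair of arms fits worse (84.1% against 97.1%). Four looks were then simulated (400,000 replicates), with dropout applied as n(1 − d):

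| n = 500 per arm | Table 2 | Constant boundary, z = 2.361 | O'Brien-Fleming type |
|---|---|---|---|
| 0.30, no dropout | 71.2% | 71.7% | 78.9% |
| 0.45, no dropout | 97.1% | 97.3% | 98.5% |
| 0.30, 10% dropout | 66.1% | 66.8% | 74.5% |
| 0.45, 10% dropout | 95.4% | 95.7% | 97.6% |
| Zero effect | 2.5% | 2.5% | 2.5% |

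The constant boundary (posterior probability about 0.991) matches every cell checked, at 0% and 10% dropout and all four sample sizes, to within about 1 point. So the 0.025 already allows for the three looks, with the maximum fixed.

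**Step 2: what a changed maximum does.** Assumptions: one increase, at the 75% look (375 per arm), to at most 750 or 1,000 per arm; boundaries unchanged; no adjusted test; no binding futility stop. Let S be the cumulative null statistic at 375 per arm, scaled to variance 375. For a trial not yet stopped, the chance of crossing at final size N is

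1 − Φ((c√N − S)/√(N − 375)),

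where c is the final boundary. The total error is the early-crossing probability plus the average of this over the trials not stopped. External means N is set without regard to S. Adversarial means N is chosen between 500 and the cap to maximise the expression. From 300,000 replicates:

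| Boundary | No change | External, 750 / 1,000 | Adversarial, 750 / 1,000 |
|---|---|---|---|
| Constant, 2.361 | 0.0253 | 0.0272 / 0.0280 | 0.0278 / 0.0290 |
| O'Brien-Fleming type | 0.0252 | 0.0279 / 0.0290 | 0.0305 / 0.0331 |
| Final test only, 1.96 | 0.0251 | 0.0251 / 0.0251 | 0.0312 / 0.0342 |

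An external increase matters under a sequential boundary because it shifts the look times: 375 of 500 is 75%, while 375 of 750 is 50%. The correlation between the third look and the final test falls from √0.75 = 0.87 to √0.50 = 0.71, so the same boundaries are crossed somewhat more often.

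For a single final test at 1.96, moving the adversarial change to the 25% or 50% look gives 0.0274–0.0288 and 0.0290–0.0311.

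**The case against.** The strongest reply is that the protocol does have controls. Section 3.1 says the thresholds are calibrated by simulation, Section 12.4 and the Overview fix the decision rules in advance, and the DMC's plan predates the trial. Section 12.3 bases the advice on global and epidemiological data, and its next sentence is about following the literature. It speaks of recommendations only, and Section 16.2 requires Steering Committee and regulatory or ethics approval for protocol changes. A sample-size rule may also sit in the SAP or DMC charter, which are not at hand.

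Most of this stands, and it rules out two stronger readings that a reader might infer.
- **That the 0.025 is unprotected, with boundaries open until after the looks.** Testing at nominal 0.025 at all four analyses would give about 0.063, but Section 3.1 states calibrated thresholds and Table 2 reproduces with them. That figure does not apply here.
- **That the error could reach 0.062.** This is 0.025 + exp(−1.96²/2)/4 = 0.0616. It is the theoretical bound for one uncapped change, with the least favourable size chosen at every interim value and a conventional final test. It does not describe this design.

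What the reply does not remove is the contradiction in the text. An unseen rule cannot reconcile two protocol statements that assign the maximum sample size differently. The words for global or overall data do not exclude the trial's own results. The calibration in Section 3.1 does not cover a change of maximum made outside it. The DMC's pre-approved plan is not identified as the SAP that holds the stopping rules.

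**Conclusion.** The point holds as a contradiction about who controls the sample size and when the rules are fixed. It does not show that the error rate has been lost. The 0.025 is calibrated for a fixed maximum of 500 per arm with three looks, and Section 12.3 permits advice that would take the trial outside that calibration.

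The effect would be moderate: one-sided error of about 0.025–0.029 for an externally driven increase and 0.028–0.034 for an adversarial one, a rise of at most about 0.9 percentage points. Under the constant boundary that fits Table 2, the worst case examined is 0.029. If the maximum stays at 500, the error is 0.025.

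The 750–1,000 per arm, the single change at the 75% look and the unadjusted boundaries are assumptions. Decreases and repeated changes were not examined.

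**What to change.** - **Section 12.3:** limit the unblinded statistician to applying the pre-specified efficacy and futility thresholds. Let any change to 500 per arm be proposed only by the blinded statisticians, from pooled or external data, with the thresholds re-simulated for the new maximum. Alternatively, pre-specify before the first look a re-estimation rule with an adjusted test, which would also control the error.
- **Overview (Sample Size row):** say what the statistician's recommendations may concern, consistently with Section 12.3.
- **Section 12.4 and Overview (Statistical Methods):** require the detailed plan before the first interim analysis instead of before database lock, and use one tense for the SAP's status. If the SAP or DMC charter already holds a dated rule, cite it.

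The cost is a wording amendment and earlier SAP sign-off. The DMC statistician also loses an informal advisory role on sample size.

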12.4 Statistical analysis and reporting

The analysis and reporting of results follow the CONSORT guidelines (www.consort-statement.org). The participant selection process and flow throughout the study will be summarized

using a flow diagram. The results of the analysis of participants' demographic data and baseline outcome variables (primary and secondary) will be summarized using descriptive summary measures: expressed as mean (standard deviation) or median (minimum-maximum) for continuous variables, as appropriate, and number (percentage) for categorical variables. We will adopt an intention-to-treat principle to analyze all outcomes.

Bayesian statistics is the standard statistical framework. Statistical analyses of IPs are limited to simultaneously randomized controlled data. Sequential designs with Bayesian stopping rules are expected to be used to evaluate multiple IPs. Recruitment for an IP will be stopped before the maximum sample size using pre-specified decision rules. The maximum sample size and corresponding decision rules are determined a priori by dedicated statisticians and methodologists, who will remain blinded during the conduct of the study. The statistical analysis plan (SAP) will be formulated to ensure that the expected one-sided Type I error is less than 0.025 for each treatment. We will also use multiple imputation to handle missing data. For all models, results will be expressed as the effect reported as the mean difference for continuous outcomes, odds ratios (OR) for binary outcomes, and hazard ratios (HR) for time-to-event outcomes, with their respective 95% confidence or credibility intervals.

All analyses will be performed using the latest version of R at the time of analysis. A detailed analysis plan will be developed prior to database lock. Any relevant safety data specific to Brazil will be immediately reported to our group for appropriate regulatory action.

12.5 Analysis of primary and secondary outcomes

To analyze the primary outcome of the mean fatigue score at day 90 as measured by the Fatigue Severity Scale, we will use the Bayesian normal-normal model with non-informative prior distributions for the group means. This analysis will be adjusted for prespecified covariates. For all other continuous outcomes, we will use similar modeling approaches. For all binary outcomes, we will use logistic regression for analysis. The Cox proportional hazards model will be used for all time-to-event outcomes. All analyses of secondary outcomes will be exploratory in nature, without adjustment for alpha across multiple secondary analyses.

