Title:	“A multicenter, adaptive, randomized, double-blind, placebo-controlled, prospective study of pharmacological interventions in participants with a clinical presentation consistent with Long COVID-19: The REVIVE-TOGETHER Protocol”
Abbreviated Title:	Long COVID Chronic Fatigue Syndrome
Investigational product:	Metformin, Fluvoxamine
Indication:	Long COVID with chronic fatigue syndrome
Phase:	PHASE III – New indication
Sponsor:	CARDRESEARCH - Cardiology Care and Research, LLC
Study code	LONG-COVID_REVIVE_TOGETHER
Principal Investigators:	[name], [name], [name], [name], [name]
Proposing institution:	Cardresearch - Cardiology Care and Research, LLC
Collaborating Researchers Scientists	[name], PhD. [name] [name]
Objectives:	
The primary objective is to compare metformin, fluvoxamine, and placebo for the mean Fatigue Severity Scale (FSS) score at 60 days after randomization. The secondary objectives are:
 
 1. To compare metformin, fluvoxamine, and placebo for the mean FFS score 30 days after randomization. 2. To compare metformin, fluvoxamine, and placebo for the mean FSS score 90 days after randomization. 3. To compare metformin, fluvoxamine, and placebo regarding the mean difference in change in health-related quality of life (EQ-5D-5L) at 60 days after randomization. 4. Compare metformin, fluvoxamine, and placebo for the odds ratio of all-cause mortality at 60 days after randomization. 5. Compare metformin, fluvoxamine, and placebo for the odds ratio of unexpected hospitalization from all causes at 60 days. 6. To assess the safety of metformin and fluvoxamine in this population of participants. 7. To assess the medium-term effects (90 and 180 days) of the investigational medical products on the chronic fatigue scale (FSS scale) and quality of life (EQ-5D-5L).
Design:	A multicenter, double-blind, adaptive, prospective, randomized, parallel-group, placebo-controlled study evaluating metformin and fluvoxamine with a 90-day follow-up after randomization.
Inclusion Criteria	Participants must meet all of the following criteria to be eligible for participation in this study:

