	
 12. Pregnant women or women of childbearing age who do not agree to use an effective method of contraception for 90 days from the date of signing this consent form; 13. Women who are breastfeeding; 14. Expected hospitalization for elective surgical procedures lasting more than 48 hours; 15. Contraindications for the METFORMIN arm 
 a. Participants currently taking metformin; b. Participants with creatinine clearance < 30 ml/min, a history of KIDIGO IV, or currently undergoing dialysis. 16. Contraindications for the FLUVOXAMINE arm 
 a. Use of serotonin reuptake inhibitors (donepezil, fluoxetine, escitalopram, paroxetine); 17. Current severe comorbid psychiatric disorder (e.g., clinical depression, anxiety, sleep disorder, eating disorder, substance abuse) that is uncontrolled and associated with significant symptoms or requiring the use of a medication contraindicated in this study; 18. Clinical history of moderate to severe hepatic impairment or hepatic cirrhosis with a Child-Pugh score of C or higher; 19. Clinical history of severe chronic lung disease with significant limitation of activities; 20. Inability of the participant to provide informed consent or adhere to the procedures proposed in the study; 21. Taking medications known to cause chronic fatigue as a side effect (except for participants with chronic cardiovascular disease who are on chronic beta-blocker therapy); 22. Known hypersensitivity and/or intolerance to fluvoxamine or metformin; 23. Any clinical condition that, in the investigator's opinion, may preclude participation in this study.
Primary and secondary outcomes:	
The primary outcome is a reduction in the FSS score of at least one standard deviation 60 days after randomization.
 
The secondary outcomes are:
 
 1. The FFS score 30 days after randomization. 2. The FFS score 90 days after randomization. 3. HRQL, assessed using the EuroQol-5D-5L 60 days after randomization. 4. All-cause mortality up to 60 days after randomization. 5. Unexpected hospitalization from any cause up to 60 days after randomization. 6. Safety and tolerability of the investigational products 7. Adverse events experienced by participants during treatment
Procedures	Screening procedures

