Bayesian statistics is the standard statistical framework for this study. Statistical analyses of IPs are limited to concomitantly randomized controlled data. Sequential designs with Bayesian stopping rules are expected to be used to evaluate multiple IPs. Recruitment for an IP will be stopped before the maximum sample size using decision rules pre-specified in the statistical analysis plan (SAP). The maximum sample size and corresponding decision rules are determined a priori by dedicated statisticians and methodologists, who will remain blinded during the conduct of the study. The statistical analysis plan (SAP) was formulated to ensure that the expected one-sided Type I error is less than 0.025 for each treatment. We will also use multiple imputation to handle missing data. For all models, results will be expressed as the effect reported as the mean difference for continuous outcomes, odds ratios (OR) for binary outcomes, and hazard ratios (HR) for time-to-event outcomes, with their respective 95% confidence or credibility intervals.

All analyses will be performed using the latest version of R at the time of analysis. A detailed analysis plan will be developed prior to database lock. Any relevant safety data specific to Brazil will be immediately reported to our group for appropriate regulatory action.

The 90- and 180-day visits are post-study follow-up visits. The primary and secondary outcomes of the study are planned to be based on the D60 visit after randomization.

Analysis of Primary and Secondary Outcomes

To analyze the primary outcome of the mean fatigue score at day 60 measured by the Fatigue Severity Scale, we will use the Bayesian normal-normal model with non-informative prior distributions for the group means. This analysis will be adjusted for prespecified covariates. For all other continuous outcomes, we will use similar modeling approaches. For all binary outcomes, we will use logistic regression for analysis. The Cox proportional hazards model will be used for all time-to-event outcomes. All analyses of secondary outcomes will be exploratory in nature, without adjustment for alpha for multiple secondary analyses.

Sensitivity Analyses

We will perform several sensitivity analyses to assess the robustness of the results, particularly for the primary outcome. These include:

1. Protocol analysis based only on participants who adhered to the protocol as described;

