2.1 Objectives/Primary Outcome

The primary objective is to compare the use of Fluvoxamine and Metformin with placebo for the mean score on the Fatigue Severity Scale (FSS) on day 60 after randomization by at least 1 point.

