2.2 Secondary objectives/ outcomes

The secondary objectives are:

- To compare fluvoxamine and metformin with placebo for the mean FFS score 30 days after randomization.
- To compare fluvoxamine and metformin with placebo for the mean FSS score 60 days after randomization.
- To compare fluvoxamine and metformin with placebo regarding the mean difference in the change in health-related quality of life (HRQL) as measured by the EQ-5D-5L at 60 days from randomization.
- Compare fluvoxamine and metformin with placebo for the odds ratio of all-cause mortality at 60 days after randomization.
- Compare fluvoxamine plus metformin with placebo for the odds ratio of unexpected hospitalization from all causes at 60 days.
- To assess the safety of fluvoxamine and metformin in this population of participants.
- To evaluate the mid-term post-study effects (90 and 180 days) of the investigational medicinal products on the chronic fatigue scale (FSS scale) and quality of life (EQ-5D-5L).

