12.11 Summary table of analyses from the website

Result	Hypothesis	Outcome Measure	Statistical analysis method
Primary Mean score measured by the fatigue severity scale on day 60 after randomization	Drug treatment will be better than placebo	Fatigue Severity Scale	Bayesian Normal-Normal analysis
Secondary Mean score measured by the fatigue severity scale on day 30 after randomization	Drug treatment will be better than placebo	Fatigue Severity Scale	Bayesian Normal-Normal Analysis
Mean score measured by the fatigue severity scale on day 90 after randomization	Drug treatment will be better than placebo	Fatigue Severity Scale	Bayesian Normal-Normal Analysis
Health-related quality of life on day 60 after randomization	Drug treatment will be better than placebo		Bayesian Normal-Normal Analysis
All-cause mortality by day 60 after randomization	Treatment will prevent overall mortality	Measuring deaths in the groups	Logistic regression
Time to all-cause mortality up to day 60 after randomization	The treatment will prevent overall mortality	Interval in days between randomization and mortality	Cox regression
Unexpected hospitalization from any cause by day 60 after randomization	The treatment will prevent hospitalization	Measurement of deaths in the groups	Logistic regression
Unexpected hospitalization for any cause up to day 60 after randomization	The treatment will prevent hospitalization	Interval in days between randomization and mortality	Cox regression
Safety of the IP	The drugs are safe in participants with long COVID	Measurement of adverse events in treatment groups	Descriptive analysis
3) Subgroup analysis: i) Age (young vs. elderly) (ii) Sex (male vs. female) female)	Older adults are at higher risk of complications Men are at higher risk	Risk assessment	Regression methods with appropriate interaction terms.

iv) Vaccination status	Unvaccinated individuals are at higher risk		
v) Obesity	Obesity carries a higher risk		
vi) Diabetes	Diabetes carries a higher risk		
vii) Hypertension			
viii) Cardiovascular disease	People with high blood pressure are at higher risk		
ix) Chronic lung disease	Lung disease carries a higher risk		
4) Sensitivity analysis	The results remain robust	Primary and key secondary outcomes (fatigue score at day 30 and day 60)	

IMPORTANT NOTES:
 
 In all analyses, results will be expressed as estimated effects with corresponding 95% uncertainty estimates 			

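### Section 12.5 sets the primary fatigue analysis at day 90, contradicting day 60 in the Overview and sections 2.1, 12.3 and 12.11; power is stated for day 60 only

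*Protocol*

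**What the plan says.** Section 12.5 ties the Bayesian normal-normal model to day 90: "To analyze the primary outcome of the mean fatigue score at day 90 as measured by the Fatigue Severity Scale". The Overview has a nearly identical paragraph with the other day: "To analyze the primary outcome of the mean fatigue score at day 60 measured by the Fatigue Severity Scale".

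Other places that fix the primary time point:
- Overview, objectives: to "compare metformin, fluvoxamine, and placebo for the mean Fatigue Severity Scale (FSS) score at 60 days after randomization".
- Overview, outcomes: "The primary outcome is a reduction in the FSS score of at least one standard deviation 60 days after randomization".
- Overview, statistical methods: "The primary and secondary outcomes of the study are planned to be based on the D60 visit after randomization". The 90- and 180-day visits are described there as post-study follow-up.
- Section 2.1: "mean score on the Fatigue Severity Scale (FSS) on day 60 after randomization by at least 1 point".
- Section 12.3: the operating characteristics in Table 2 are for the day-60 mean score.
- Section 12.11, primary row: "Mean score measured by the fatigue severity scale on day 60 after randomization". The day-90 score has its own row under the secondary outcomes.

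Section 2.2 lists as its second secondary objective: "To compare fluvoxamine and metformin with placebo for the mean FSS score 60 days after randomization". Day 90 appears in that list only in the item on medium-term effects at 90 and 180 days.

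**The concern.** The day-60 score is taken at the end of the 60-day course. The day-90 score is taken 30 days later, so it measures whether an effect persists off treatment. These are different questions, and a phase III trial needs one of them fixed as primary.

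The conflicting day stands in the body section that tells the analyst which score enters the primary model. Section 2.2 reinforces it: someone who read only 2.2 and 12.5 would find day 60 listed as secondary and day 90 as primary. Section 4.1 also describes the D90 and D180 visits as an open-label phase, which is a weaker setting for a self-reported primary outcome. The protocol gives no SD, effect, dropout rate or power for day 90.

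**Working it through.** **1. The texts side by side**

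| Place in the Protocol | Primary FSS day | Day-90 FSS or visit |
|---|---|---|
| Overview, objectives and outcomes | 60 | secondary |
| Overview, sample size | 60 | not mentioned |
| Overview, statistical methods | 60 | post-study visit |
| Section 2.1 | 60 | not mentioned |
| Section 2.2 | (lists day 60 as secondary) | only in the 90/180-day item |
| Section 12.3, Table 2 | 60 | not mentioned |
| Section 12.5 | **90** | primary |
| Section 12.11, outcome rows | 60 | secondary |

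Two further places are unclear. The sensitivity row of 12.11 puts day 30 and day 60 in one parenthesis after the words for primary and key secondary outcomes, so day 60 can be read as key secondary. The flowchart note in 3.1 names D90 as the outcome visit, where the same note in the Overview names D60. The 3.1 note also calls D90 the post-study visit, so it contradicts itself; this may be an error in reading the figure and carries no weight here.

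**2. Timing and blinding.** Treatment lasts 60 days (6.3), and 90 − 60 = 30 days off treatment, as 8.5 confirms. Section 4.1 calls this phase post-study and open-label. Section 6.1, however, keeps allocation confidential until the database is finalized after the last scheduled follow-up.

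**3. Which day the stated power belongs to.** Inputs from 12.3: SD 1.7, difference 0.45, one-sided alpha 0.025, 500 per arm, 10% dropout. Table 2 gives 95.4%.
- Fixed sample: n = 500 × 0.9 = 450 per arm; SE = 1.7 × √(2/450) = 0.1133; 0.45/0.1133 = 3.97; power = Φ(3.97 − 1.96) = Φ(2.01) = 97.8%. This is above the stated 90% but 2.4 points over the Table 2 cell.
- With looks at 25%, 50%, 75% and 100% and a constant efficacy threshold of z ≈ 2.37, calibrated by simulation to overall alpha 0.025: 95.7%, against 95.4% in the table. At 0% dropout the same rule gives 97.3% against 97.1% (difference 0.45) and 71.5% against 71.2% (difference 0.30). The constant threshold is an assumption, since the protocol does not state its thresholds.

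The stated power therefore reproduces, and 12.3 labels it as day 60.

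**4. What day 90 could mean for power.** All inputs here are assumed.
- Same effect and SD as day 60, fixed sample: 97.8%, 96.3% and 93.8% at 10%, 20% and 30% dropout.
- Faded effect, read from Table 2 at 10% dropout and n = 500: 95.4% with no fade; 66.1% if one third is lost (0.45 to 0.30); 20.6% if two thirds are lost (0.45 to 0.15).

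**5. If both days were tested and the better one claimed.** For a single fixed look, the one-sided type I error per comparison is 1 − Φ₂(1.96, 1.96; ρ). It is 0.0454, 0.0417 and 0.0390 for an assumed correlation ρ between the two scores of 0.5, 0.7 and 0.8.

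**The case against.** The strongest reply is that this is one wrong number. The parallel Overview paragraph is almost identical and says day 60, and the Overview states that outcomes rest on the D60 visit. It also lists day-90 FSS as secondary, as does 12.11. No clause ranks the body above the Overview, and the statistical analysis plan, not shown here, may already settle the matter. Most of this stands: day 60 is plainly intended. It does not remove the error, because the protocol states the wrong day in its own primary-analysis section, and a correct analysis plan would then contradict the protocol.

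Three stronger readings are tempting but not supported:
- **Two primary analyses are pre-specified, so type I error rises to about 0.039–0.045.** No passage allows both days to be tested and the better one chosen. The figures also assume a correlation and a single fixed look, although three interim analyses are planned.
- **Power falls to 66.1%.** That rests on one assumed fade. With no fade, the same SD and the same dropout, power at day 90 is unchanged.
- **Day-90 scores would be unblinded.** Section 4.1 says open-label, but 6.1 keeps allocation confidential until the database is finalized. The two do not agree, so bias at day 90 cannot be concluded.

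**Conclusion.** Section 12.5 is wrong as written and must be corrected. It names a primary time point that conflicts with the Overview and sections 2.1, 12.3 and 12.11, and section 2.2 compounds the conflict by listing the day-60 score as secondary. This is a textual contradiction, not an arithmetic error: the day-60 power reproduces closely (95.7% against 95.4%, under an assumed constant threshold).

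Taken literally, 12.5 would base the primary conclusion on a visit 30 days after the end of treatment for which the protocol states no operating characteristics. The harm cannot be quantified from the document. The power and type I figures for day 90 are illustrations under assumptions, and the conclusion does not depend on them. The differing endpoint wordings in the Overview (one standard deviation) and section 2.1 (1 point) are a separate matter; both stay at day 60.

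**What to change.** 1. Section 12.5: replace day 90 with day 60.
2. Section 2.2, second bullet: replace 60 days with 90 days, matching the secondary objectives and outcomes in the Overview and the secondary row in 12.11.
3. Section 12.11, sensitivity row: reword it so that day 60 is the primary FSS time point and days 30 and 90 are the key secondary ones.
4. Section 3.1, flowchart note: check against the source that D60 is named as the outcome visit, as in the Overview flowchart note, and correct it if it is not.

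Nothing further on interim rules is needed for this point, since the Overview leaves decision rules to the statistical analysis plan.

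The cost is three wording changes and one check, made through the amendment route in 16.2. Sample size, power, visits and data collection stay as they are.
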